11.1 Sample

Phase III studies are usually randomized, often with one group receiving the current standard treatment. These studies may or may not be placebo-controlled. However, the population with co-infection with HCV and HIV is difficult to treat and has very few treatment options. In this population, the use of a standard care group is difficult to justify ethically because response rates with such a regimen are low and because the toxicity of the current standard of care (i.e., PEGIFN + RBV) is considerable.

In this regard, we could establish that SVR in the historical control group is between 10% (95% confidence interval [CI]: 5%-18%) in previously treated patients and 26% described in the placebo control group in the phase II study of patients infected with HCV and not previously treated with boceprevir.

11.2 Sample size

The primary objective of this study is to estimate SVR with response-guided therapy with boceprevir in patients with controlled HIV infection and chronic hepatitis C with genotype 1 virus in whom prior treatment with peginterferon/ribavirin has failed.

Since no comparative analysis is to be performed, the sample size depends on the accuracy of the SVR calculation. SVR from double treatment with peginterferon and ribavirin ranges from 27% to 39%.

The expected SVR with boceprevir triple therapy is 60%. If we define a margin of error ($60\% \pm 8.5\%$) that encompasses the maximum SVR observed with dual therapy (39%), the required sample size based on a bilateral 95% confidence interval is 128 patients.

The sample size calculation for the different RVM values was based on a bilateral 95% confidence interval for different levels of accuracy.

Stratification

Since this is a non-randomized study, no stratification is planned; however, for the purposes of data analysis, patients will be classified according to the type of failure of previous HCV treatment (no response, virologic rebound, and relapse).

No response: HCV RNA positivity at week 12.

1. Partial response. Patients who achieved at least a reduction in HCV RNA of two logarithmic units from baseline at week 12 but still had viremia at the end of treatment.
2. Null response. Patients who did not achieve a reduction of two logarithmic units of HCV RNA at week 12.

Rebound: negativity for HCV RNA at week 12, but positivity before week 48.

Relapse: HCV RNA undetectable at the end of treatment and subsequently detectable during 24 weeks of follow-up.

As this is an exploratory study, the inclusion of difficult-to-treat patients, such as those with no response (reduction in HCV RNA of less than two log units with prior HCV treatment) or with cirrhosis, will be limited to 30% of the study population.

11.3 Analysis

In this open study, all variables will be tabulated. Quantitative variables will be described by the number of available and omitted observations, the mean, the median, the standard deviation, the interval (minimum and maximum) and the first and third quartiles. Of the qualitative variables, the frequency and percentage will be presented. Omitted values will be tabulated with their frequency, but will not be included in the calculation of the percentages.

The primary endpoint will be assessed with a bilateral CI of 95% around the observed proportion of SVR. The analysis of the primary endpoint in SVR will be carried out in two ways. Patients who withdrew from the study within the first four weeks will be included in the main analysis, which will be counted as SVR failures. As a secondary analysis, an SVR analysis will also be performed, but restricted to patients who have not withdrawn from the study in the bitherapy period in the first four weeks. In both analyses, patients in whom SVR data are lacking due to premature withdrawal from the study at any time after the initial bitherapy period of the first four weeks will be included and counted as SVR failures.

Inferential analysis of boceprevir efficacy will be assessed by SVR at week 24 and the 95% confidence interval. A similar analysis will be applied to evaluate the secondary variables. For continuous quantitative variables, the mean or median and the 95% confidence interval or the interquartile interval shall be calculated.

Descriptive analyses of treatment-occurring adverse events and treatment-occurring adverse events that are possibly or likely related to the study drug will be performed. With regard to the safety assessment in the AEs, the 95% CI of the percentage of grade 3 or higher adverse events and other serious adverse events reported by the centres shall be provided. The highest grade episode per person over time will be used. Descriptive tables will be provided summarizing the events and the number of people who have presented the events by grade.

Variations in HIV-1 viral load or RNA and CD4+ T cell count at each post-enrollment visit will be summarized. The rates and reasons for premature discontinuation of treatment, including HCV treatment failures, will be summarized.

In addition, a logistic regression analysis will be carried out taking SVR as a dependent variable. The importance of the previously identified prognostic factors will be confirmed by univariate logistic regression. The independence of these factors will then be evaluated using a stepwise method in which the factors that were significant in the univariate analyses will be used.

All analyses will be bilateral and will have a significance level of 5%. The following variables will be analyzed:

Efficacy: sustained virologic response, virologic response at weeks 4, 8, 12, and 24.

Safety: All adverse events, whether or not related to the study medication.

HCV resistance following BOC-containing treatment in patients with virologic failure.

* Predictive factors of SVR: SVR will be analyzed by subgroups according to sex, age, degree of fibrosis at baseline, previous null response, CD4 lymphocyte count at baseline, greater or lesser decrease of one logarithmic unit of HCV RNA at week 4, undetectable HCV RNA at week 8, and pharmacogenetic markers

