1.4. Principal Investigator and Study Coordinator: [name] [name]

Collaborating researchers: [name] [name].

1.5. Centres in which the trial is planned to be carried out:

The centres where the trial is planned to be carried out are detailed in the document "*List of participating centres and researchers*".

1.6. Clinical Research Ethics Committees that have approved the trial:

The trial has been presented to all the CEICs corresponding to the participating centers, and the CEIC of the Hospital Clínic de Barcelona has also been assigned as a reference CEIC.

1.7. Name and qualification of the person responsible for monitoring:

[name].
Clinical Trials Unit.
CTU Clinic. Clinical Pharmacology Service.
(Hospital Clínic de Barcelona).
Head of the CTU: [name] [name]

1.8. Study drug information:

Boceprevir: The drug has final approval by the Ministry of Health. As stated in its technical sheet (see annexes).

1.9. Phase of the clinical trial: Phase III.

1.10. Objectives:

1.10.1. Main objective:

The primary objective of this study is to evaluate the safety and efficacy of response-guided therapy with boceprevir 800 mg three times daily orally (o.v.) in combination with peginterferon (alpha-2b or alpha-2a) and ribavirin in genotype 1 HIV- and HCV-infected patients in whom prior HCV treatment with ribavirin-associated pegylated interferon had failed.

1.10.2. Secondary objectives:

- To define predictors of sustained virologic response (SVR), such as epidemiological factors, disease characteristics, clinical status of HIV infection, and response during treatment, especially at weeks 4, 8, 12, and at the end of treatment.
- To determine the percentage of patients with undetectable HCV RNA at treatment weeks (ST) 4, 8, and 12 and at the end of treatment.
- Evaluate virologic response based on baseline characteristics
- To investigate HCV resistance following virological failure with a regimen containing boceprevir (BOC). Blood samples should be obtained at baseline, at the time of virological failure (VF) (VF: two consecutive samples with signs of HCV replication after HCV was undetectable – below the lower limit of detection – or HCV RNA rebound equal to or greater than one logarithmic unit with respect to the RNA nadir) and six months after virological failure. The evaluation of resistance will be carried out in a single center (coordinating center: Hospital Clínic, Barcelona) by means of population sequencing of the genome that encodes the HCV protease.

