The primary efficacy endpoint is the achievement of SVR, defined as an undetectable plasma HCV RNA at follow-up week (SS) 24.

If SS24 data are not available in a patient and the HCV RNA in SS12 is undetectable, SVR will be considered to be present.

Rules of futility:

HCV treatment failure is defined as follows:

- HCV RNA in serum >100 IU/mL at week 12
 - Or
 - Confirmed increase in serum HCV RNA to >1,000 IU/mL at any time after week 12
 - Or
 - detectable HCV RNA (above the lower limit of detection of HCV assay COBAS® Taqman® v2.0. de Roche) in week 24

Secondary endpoints:

- Percentage of patients with virologic response (HCV RNA undetectable at weeks 4, 8, or 12) in those who achieve SVR.
- Percentage of patients with HCV RNA undetectable in SS12.
- Percentage of patients with undetectable HCV RNA 72 weeks after randomization.
- HCV resistance after treatment with BOC-containing therapy. Blood samples will be obtained at baseline and after HCV virological failure, and at the end of the study a resistance analysis will be performed in a single center (Hospital Clínic, Barcelona).
- Safety.

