6.6 Termination and/or Discontinuation Criteria

The treatment will be **compulsorily** terminated during the study for any of the following reasons:

- Patient with HCV RNA >100 IU/mL in ST12 or detectable HCV RNA in ST24.
- Suicide or homicide thoughts or attempts.
- Severe depression or major depressive episode.
- Positive test result for non-prescription opioids, methamphetamines, or cocaine.
- Pregnancy during the study.
- Virological rebound, defined as:

Any patient who obtains an undetectable HCV RNA and subsequently presents an HCV RNA > 1,000 IU/ml.

Once virologic rebound has been identified, genotypic resistance will be characterized by HCV RNA sequencing in suitable samples, such as those collected at the time of rebound and during the follow-up period.

Treatment **may** be terminated during the study for any of the following reasons:

- The medical investigator determines that a SAE is possibly or likely related to the study drug.
- Failure to administer, evaluate, or other study requirements.

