7.3 Withdrawal criteria

Treatment with the study drug will be terminated **immediately** during the study for any of the following reasons:

- Patient with HCV RNA >100 IU/mL in ST12 or detectable HCV RNA in ST24.
- Suicide or homicide thoughts or attempts.
- Major depression, major depressive episode.
- Positive test result for non-prescription opioids, methamphetamines, or cocaine.
- Pregnancy during the study.
- Express wish of the patient
- Virological rebound, defined as:

Any patient who obtains an undetectable HCV RNA and subsequently presents an HCV RNA > 1,000 IU/ml.

Once virologic failure has been identified, genotypic resistance will be characterized by HCV RNA sequencing in suitable samples, such as those collected at the time of failure and during the follow-up period.

Treatment with the study drug **may** be terminated during the study for any of the following reasons:

- The medical investigator determines that a SAE is possibly or likely related to the study drug.
- Failure to administer, evaluate, or other study requirements.

8. Treatment of Subjects

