11.5 Processing of lost data

Missing data imputation techniques will not be used. Only the available data will be analyzed.

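### Patients compulsorily stopped for virological failure at week 12 have no assigned week-24 outcome, so the omitted-values rule would drop them from the week-24 response percentage and bias it upward

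*Combined protocol and SAP*

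**What the plan says.** The variable list in section 11.3 reads "Efficacy: sustained virologic response, virologic response at weeks 4, 8, 12, and 24". Week 24 therefore stands beside the on-treatment weeks 4, 8 and 12 and apart from SVR. The visit table in section 17 schedules HCV RNA at Day 1 and at ST4, ST8, ST12, ST24 and ST48, where ST means week of treatment (section 1.10.2).

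Section 6.6 makes stopping compulsory for this case: "Patient with HCV RNA >100 IU/mL in ST12 or detectable HCV RNA in ST24". Section 7.3 repeats the criterion under the words "Treatment with the study drug will be terminated". The futility rules in section 6.1 classify the same finding as HCV treatment failure: "HCV RNA in serum >100 IU/mL at week 12".

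On missing values, section 11.3 states: "Omitted values will be tabulated with their frequency, but will not be included in the calculation of the percentages". Section 11.5 states: "Missing data imputation techniques will not be used. Only the available data will be analyzed". The one rule that counts missing as failure is also in section 11.3. It is written for patients whose SVR data are lacking because they left the study prematurely.

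**The concern.** A patient stopped at ST12 for HCV RNA above 100 IU/mL is a known failure and has, on the face of the plan, no ST24 visit. The gap at week 24 is then created by the protocol and decided by the outcome. Treating it as an ordinary omitted value removes failures only and keeps every responder.

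The week-24 percentage would then describe response among patients who had already passed the week-12 virological test. The same patients do have an ST12 value, so they count in the week-12 percentage. Read side by side, the two figures could show response rising from week 12 to week 24 only because failures had been excluded. The stake is the correct reading of one listed efficacy variable, not the main conclusion of the trial.

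**Working it through.** **The plan's own figure.** Section 11.2 gives 128 patients for a two-sided 95% interval of 60% ± 8.5 points. The formula n = z² p(1-p)/d² with z = 1.96, p = 0.60 and d = 0.085 gives 127.6, which rounds up to 128. The figure reproduces, so N = 128 is used below.

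**Inputs that the documents do not give.** There is no stated number of patients stopped at week 12 and no stated week-24 response rate. Both are assumed. Let R be the number undetectable at week 24, and m the number of non-responders with no ST24 value because treatment had already stopped.

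**Formulas.**
- All included patients, stopped patients counted as non-responders: R/128.
- Available data only: R/(128-m).
- Relative inflation: [R/(128-m)] / [R/128] - 1 = m/(128-m), which does not depend on R.

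For any m of 1 or more, the second rate exceeds the first, so the bias can only be upward. With m = 11 the relative inflation is 11/117 = 9.4%; with m = 12 it is 12/116 = 10.3%.

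**Size in percentage points.** Since m cannot exceed the number of non-responders, each block takes about a quarter and about a half of them.

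| Assumed week-24 response | Non-responders | m | Available-data rate | Bias (points) |
|---|---|---|---|---|
| 77/128 = 60.2% | 51 | 13 | 77/115 = 67.0% | +6.8 |
| 77/128 = 60.2% | 51 | 26 | 77/102 = 75.5% | +15.3 |
| 96/128 = 75.0% | 32 | 8 | 96/120 = 80.0% | +5.0 |
| 96/128 = 75.0% | 32 | 16 | 96/112 = 85.7% | +10.7 |

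The first block borrows the 60% that section 11.2 expects for SVR. Week-24 on-treatment response should be higher than SVR, because some patients will rebound later or relapse after treatment. The second block allows for that with an assumed 75%.

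**Yardstick.** The ± 8.5 points was set for SVR, but it shows scale. The bias is below it with 13 missing (60% block) or 8 missing (75% block), and above it with 26 or 16 missing.

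**Comparability with week 12.** Suppose the same 96 patients are undetectable at weeks 12 and 24, all 128 have an ST12 value, and 16 are stopped at ST12. The plan's rules would report 75.0% at week 12 and 85.7% at week 24, although no patient's status had changed.

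**The case against.** Several points on the other side have force.

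- **Week 24 is peripheral.** The stated objectives cover "undetectable HCV RNA at treatment weeks (ST) 4, 8, and 12" and the end of treatment, and the secondary endpoints in sections 1.13.2 and 6.1 name weeks 4, 8 and 12, follow-up week 12 and week 72. Week-24 on-treatment response appears once, in the list in section 11.3. This stands, and it limits the weight of the point.
- **The SVR estimate is safe.** A reader might infer that the primary result is inflated too. The documents do not support that: the SVR analysis counts patients lost after the four-week lead-in as failures, and the week-12 finding is itself defined as treatment failure.
- **The failure rule may carry over.** Section 11.3 says that the secondary variables get a similar analysis. This could be read as extending the failure rule. However, the sentence directly follows the one on confidence intervals, says nothing about missing data, and sits against section 11.5. It leaves the matter open.
- **Stopped patients may still have a value near week 24.** The stop is of treatment, not of the study, and failures are to be sampled again six months after failure. Section 6.3 also lets peginterferon and ribavirin continue when boceprevir is stopped, although in the context of toxicity and intolerance. A sample at calendar week 24, if used, would shrink or remove the bias. No section provides for that sample or says that it counts as ST24.
- **A coder might record them as non-responders anyway,** since their failure is known. That would be sensible, but the plan does not say it.
- **The gap would be visible.** Omitted values are tabulated, and reasons for discontinuation, including HCV treatment failure, are summarised. A careful reader could rebuild the full denominator, but the headline percentage would still mislead.

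**Conclusion.** The point holds as a defect in how one listed efficacy variable is to be calculated. Under the rules as written, patients stopped at ST12 for HCV RNA above 100 IU/mL would leave the week-24 denominator. The direction of the bias is then certain. Its size is not.

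The illustrative range is about +7 to +15 points at an assumed 60% week-24 response (13 to 26 missing), and about +5 to +11 at an assumed 75% (8 to 16 missing). These figures assume that every patient without an ST24 value is a non-responder and that no later sample is substituted. Patients detectable at or below 100 IU/mL at week 12 continue treatment, are measured at ST24, and stay in the denominator.

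A reader might infer a larger distortion, such as +25 points, by setting 38 missing against the 60% figure (77/90 = 85.6%). That needs three-quarters of the 51 failures to be off treatment before ST24 and, by equating week-24 response with SVR, allows no relapse or later rebound. The plan recognises both. At 75% response only 32 patients are non-responders, so 38 missing is impossible. The documents do not support quoting that figure as the expected size.

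**What to change.** In section 11.3, with a cross-reference in section 11.5, exempt on-treatment virologic response at week 24 from the omitted-values and available-data rules. State that the denominator is all included patients. Count as non-responders those already stopped under the week-12 or rebound criteria, and those withdrawn before ST24. Report the available-data percentage only as a supplement, labelled as response among patients still on treatment at ST24, with its own denominator.

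This takes about two sentences. It needs no new data, visits or patients, and it leaves the stopping criteria and the SVR analysis as they are. The cost is that the reported week-24 rate becomes less favourable.

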11.4 Completion Criteria

The study will be considered to have been completed on the date of the last visit of the last subject recruited into the study.

11.5 Processing of lost data

Missing data imputation techniques will not be used. Only the available data will be analyzed.

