4.3 Treatment Regimen

PEG-IFN alfa-2a or 2b and ribavirin will be provided by each hospital and will be administered in accordance with the approved technical data sheets.

BOC (Boceprevir). Provided by the study sponsor.

Description:

BOC is supplied in 200 mg capsules. Each capsule contains 200 mg of BOC, sodium lauryl sulfate, microcrystalline cellulose, lactose monohydrate, croscarmellose sodium, pregelatinized starch, and magnesium stearate packaged in number 0 hard gelatin capsules. Each capsule contains approximately 56 mg of lactose monohydrate. In people with lactase deficiency, the clinical manifestations of lactose intolerance require 3 to 5 g of lactose (4 to 7 times the total amount of BOC capsules) to appear.

Route of administration: oral

Dosage: total daily 2400 mg, (12 capsules).

Storage: keep in the fridge at a temperature between 2°C and 8°C. The products of the study must be stored in a safe place with limited access and in the storage conditions specified on the supply label.

[figure not shown]
Dosage Schedule:

Boceprevir is administered three times a day using a dosing schedule of 4 capsules every 8 hours. Actual times of dose administration may be modified to fit the patient's schedule, although 7- to 9-hour

intervals between administrations should be maintained. All doses of boceprevir will be given with food (a small snack is sufficient).

Study period and treatment:

All patients will receive an initial 4 weeks of bitherapy with Peg-Interferon and ribavirin (PR).
-If there is a decrease in HCV RNA greater than 1 logarithm with respect to baseline HCV-RNA, the patient will be included in the treatment scheme detailed below.

-If the RNA drop is ≤ 1 log at week 4, PR/boceprevir will be administered for an additional 44 weeks. All cirrhotic patients will receive PR for 4 weeks, followed by RP/boceprevir for another 44 weeks

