11.7 Population under analysis

The population analyzed in the study will consist of all patients included in the study as detailed in the protocol and without major deviations from the protocol.

12. Direct Access to Source Data/Documents

The sponsor shall ensure that it is specified in the protocol or other written agreement that the investigator or institution shall allow direct access to the source data or documents for monitoring, auditing and review by the IRB as well as inspection of the trial by the competent health authorities.

13. Ethics

General considerations: The trial will be carried out in accordance with the principles emanating from the Declaration of Helsinki (See Annex *VIII*) and according to the legal regulations in force (Royal Decree 223/2004) and will not begin until the approval of the reference CEIC, the approval of the Management of all the participating centres, and the authorisation of the Spanish Agency for Medicines and Health Products have been obtained.

Information to the subjects: Patients will be informed orally and in writing and all relevant information adapted to their level of understanding will be communicated to the participants. (See *Attachment III: Patient Information Sheet/Written Consent Sheet*)

14. Data Management and Archiving of Records

The patient will be informed that their participation in the trial will be treated with the same confidentiality as their clinical documentation.

In the data collection notebook, the patient will be identified only by their inclusion code in the study.

The patient's name will not appear in any publication or communication of the results of the study.

The patient's participation in the trial will be reflected in their medical history.

The investigator will complete a list that will include the names of the patients participating in the trial, their inclusion number in the trial and their medical history.

Only researchers and data quality assurance and data analysis personnel will have access to the participant's clinical documentation. Eventually, persons duly authorised by the Sponsor and the Health Authorities and the Clinical Research Ethics Committee may audit or inspect the trial. Personal information will not be available to the public, in compliance with the provisions of Organic Law 15/1999, of 13 December, on the Protection of Personal Data.

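### The only analysed population excludes undefined major deviations, so the denominator of the primary SVR is not fixed in advance

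*Combined protocol and SAP*

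**What the plan says.** Four places in the combined protocol and SAP bear on the denominator of the primary SVR.

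- Section 11.7 gives one analysed population for the whole study: "all patients included in the study as detailed in the protocol and without major deviations from the protocol". The primary endpoint is not exempted. I find no definition of a major deviation in the supplied text, and nothing on who classifies deviations or when.
- Section 11.3 deals with withdrawals. For the four-week lead-in: "Patients who withdrew from the study within the first four weeks will be included in the main analysis, which will be counted as SVR failures". The secondary analysis is "restricted to patients who have not withdrawn from the study in the bitherapy period in the first four weeks". Both analyses include, and score as failures, "patients in whom SVR data are lacking due to premature withdrawal from the study at any time after the initial bitherapy period". The same section has a general tabulation rule: "Omitted values will be tabulated with their frequency, but will not be included in the calculation of the percentages".
- Section 11.5 has a general missing-data rule: "Missing data imputation techniques will not be used. Only the available data will be analyzed".
- Sections 1.13.1 and 6.1 add a substitution rule for follow-up weeks (SS) 24 and 12: "If SS24 data are not available in a patient and the HCV RNA in SS12 is undetectable, SVR will be considered to be present".

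**The concern.** Sections 11.3 and 11.7 point to different denominators. Keeping withdrawn patients in and scoring them as failures belongs to an analysis of all included patients. Dropping major deviators belongs to a per-protocol analysis. Section 11.3 never says that patients with deviations stay in, and 11.7 says that they go out.

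This matters because section 11.2 makes estimation of SVR the primary objective and sizes the trial on precision alone. Section 8.1 describes an open-label single arm, and section 3.7 has HCV RNA measured at each centre. Whoever decides later what counts as a major deviation may therefore know whether the patient responded. Removal raises SVR if deviators respond less often than the rest, and lowers it if they respond more often.

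A second, smaller question is what happens when SVR is missing in someone who did not withdraw. The failure rule in 11.3 is tied to withdrawal, and the SS12 rule fills a missing SS24 only as a success. What is left falls to 11.5 and the tabulation rule, both of which take the patient out of the percentage.

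**Working it through.** **Inputs.** From section 11.2: expected SVR 60%, margin 8.5 points, two-sided 95% interval, N = 128, and a dual-therapy maximum of 39%. The documents give no rate of major deviations or of SVR missing without withdrawal, so those below are assumptions.

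**1. The plan's own figure.** n = 1.96² × 0.60 × 0.40 / 0.085² = 127.6, rounded up to 128. The half-width at 128 is 1.96 × √(0.24/128) = 8.49 points. The stated sample size reproduces and is not in dispute.

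**2. Baseline.** 0.60 × 128 = 76.8, taken as 77 responders: 77/128 = 60.2%, normal-approximation 95% CI 51.7 to 68.6.

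**3. Excluding deviators under 11.7.** If a fraction f is excluded and their own SVR is s, the reported SVR becomes (0.60 - f·s)/(1 - f).

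| Excluded f | s = 0% | s = 30% | s = 60% | s = 80% |
|---|---|---|---|---|
| 5% | 63.2% (+3.2) | 61.6% (+1.6) | 60.0% (0) | 58.9% (-1.1) |
| 10% | 66.7% (+6.7) | 63.3% (+3.3) | 60.0% (0) | 57.8% (-2.2) |

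For example, f = 10% and s = 0 gives 0.60/0.90 = 66.7%.

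**4. Precision.** The half-width at 60% is 1.96 × √(0.24/n): 8.69 points at n = 122 (about 5% out) and 8.95 at n = 115 (about 10% out), against 8.49. This loss is minor.

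**5. Comparison with 39%.** The lowest interval comes from removing responders. With 13 patients removed, 10 of them responders (77%, close to the 80% column), 67/115 = 58.3% (49.2 to 67.3). Even if all 13 were responders, 64/115 = 55.7% (46.6 to 64.7). Both lower limits exceed 39%.

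**6. SVR missing without withdrawal.** The patient concerned did not withdraw, has neither an SS24 nor an SS12 result, and does not meet the treatment-failure rules in 6.1. If missing is meant to equal failure, dropping such patients from 77/128 gives:

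- one: 77/127 = 60.6% (+0.47 points)
- two: 77/126 = 61.1% (+0.95)
- three: 77/125 = 61.6% (+1.44)

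**The case against.** The best reply is that 11.3 is written for SVR and so governs over the general sections. For withdrawals that stands. A reader might infer that 11.5 drops withdrawn patients as well, but 11.3 says the opposite for this endpoint.

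A reader might also infer that patients who leave during the lead-in are major deviators because they never receive boceprevir (section 4.3: "All patients will receive an initial 4 weeks of bitherapy with Peg-Interferon and ribavirin (PR"). On that view 11.7 would make the main analysis identical to the secondary one. The documents do not support this. Section 11.3 expressly keeps those patients in the main analysis, the secondary analysis has meaning only if they differ, and section 7.3 foresees withdrawal without calling it a deviation. The reply does not reach patients who stay in the trial with a deviation, because 11.3 is silent on them.

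On missing results, the other side is largely right that few patients are affected. A detectable SS12 result with no SS24 is naturally a failure, loss to follow-up is naturally read as withdrawal, and those meeting the 6.1 rules are naturally failures. The upward shift also presumes that missing should equal failure. If the missing patients respond at 60% like everyone else, dropping them causes no bias, and scoring them as failures lowers SVR by 60 × k/128, that is 0.5, 0.9 or 1.4 points for k = 1, 2 or 3.

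Finally, section 11.2 calls the study exploratory, and 11.6 requires departures from the plan to be justified. Section 11.6 does not help here: excluding deviators under 11.7 follows the plan, so there would be no departure to justify.

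**Conclusion.** The point holds and should be fixed. The main defect is in 11.7: a single population that excludes an undefined category, with no exemption for the primary SVR. At an expected SVR of 60%, the reported value could move by +3.2 to -1.1 points with 5% excluded and by +6.7 to -2.2 with 10% excluded. The exclusion rates and the deviator SVR of 0 to 80% are assumptions. The upper end is large beside the planned 8.5-point margin, but it requires that no excluded patient responded.

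The missing-result gap is secondary and depends on how withdrawal is read. It is worth about +0.5 to +1.4 points for one to three patients, if missing is meant to equal failure.

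A reader might infer that the trial's conclusion or its sample size is at risk. Neither follows: 128 reproduces, the precision loss is under half a point in the cases sized, and no case brings the lower limit down to 39%. What is at risk is a modestly biased point estimate and a denominator that can be settled after the data are known.

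**What to change.** - In 11.3, state that the primary SVR analysis covers all included patients regardless of protocol deviations.
- In 11.3, after the SS12 rule has been applied, count as failure any SVR missing for whatever reason, and any patient with a detectable SS12 result and no SS24.
- Limit 11.5, and the 11.3 sentence on omitted values, to variables other than SVR.
- In 11.7, relabel the set as a supportive per-protocol population, and define major deviations before the analysis.
- Keep the analysis without lead-in withdrawals as the stated secondary analysis.

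The cost is wording in three sections and one definition. No patients, visits or data are added. The reported SVR may be slightly lower, since failure scoring is conservative for patients whose result is truly unknown.
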